15.2 Demographic and Baseline Characteristics

The following demographic variables at screening will be summarized: race, gender, age, height and weight.

15.3 Analysis of Primary Endpoint

Both intention-to-treat (ITT) and per-protocol analysis will be performed. All randomized, non-withdrawn patients will be included in the ITT analysis. All subjects completing the systemic temperature regulation protocol as outlined in Section 8.3 will be included in the per-protocol analysis. Subjects who had a protocol violation will be excluded from the per-protocol analysis.

The primary outcome (presence or absence of AKI) will be compared between the two arms by two-sample proportion test, furthermore, a multiple logistic regression model will be utilized where AKI status (present or absence) is considered as the outcome and arms along with demographic characteristics (e.g, race, gender, age, etc.) and clinical characteristics (such as local cooling, Model for End-Stage Liver Disease score, etiology of liver disease, etc.) are considered as predictors and/or covariates.

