12 DISCONTINUATION AND REPLACEMENT OF SUBJECTS

12.1 Early Discontinuation of Study Treatment

A subject may be discontinued from study treatment at any time if the subject, the investigator, or the surgeon feels that it is not in the subject's best interest to continue. The following is a list of possible reasons for study treatment discontinuation:

- Subject withdrawal of consent
- Adverse event that in the opinion of the investigator would be in the best interest of the subject to discontinue study treatment
- Protocol violation requiring discontinuation of study treatment

If a subject is discontinued from treatment due to an adverse event, the subject will be followed and treated by the Investigator until the abnormal parameter or symptom has resolved or stabilized.

Subjects will also be discontinued from the study treatment if the study doctor is unable to place the ECD after three attempts.

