12.4 Replacement of Subjects

Subjects who undergo early discontinuation of the study treatment will not be replaced, and such events will be accounted for by intention-to-treat analysis.

Subjects who withdraw from the study will be replaced with a new subject that will be independently randomized.

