13 PROTOCOL VIOLATIONS

A protocol violation occurs when the subject or investigator fails to adhere to significant protocol requirements affecting the inclusion, exclusion, subject safety and primary endpoint criteria. Protocol violations for this study include, but are not limited to, the following:

- Early termination of temperature management protocol
- Removal of ECD prior to the end of surgery
- Failure to pack the right kidney with ice
- Inability to maintain target temperature for ≥ 1 hour
- Failure to meet inclusion/exclusion criteria
- Failure to comply with Good Clinical Practice (GCP) guidelines will also result in a protocol violation.

Protocol violations will be accounted for by intention-to-treat analysis. Withdrawal of the subject will not be required, as all study procedures are completed within the first visit at the time of LTx.

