15.6 Sample Size and Randomization

Considering one interim analysis for efficacy, and given the incidence of AKI in LTx patients at UCSF (68%), we estimate a sample size of 101 subjects per arm (n = 202 total) is needed to detect a 30% reduction in AKI with 80% power at overall alpha = 0.05 (two-tailed).

We will aim to enroll 230 total subjects to allow for just over a 10% drop-out rate, since some subjects may not be able to complete the protocol and will be withdrawn from the study. UCSF is a high-volume center for LTx (> 180 cases per year), the majority of which meet our inclusion criteria. Thus, we estimate it will take no more than two years to complete study enrollment. The website http://www.swogstat.org was used to perform the power calculation, and the power calculation was confirmed by the CTSI at UCSF.

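### Sections 15.3 and 15.6, read together, take protocol non-completers out of the ITT set, while sections 12.4 and 13 keep them in; the primary analysis set should be reconciled

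*Combined protocol and SAP*

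**What the plan says.** Section 15.3 sets the primary population: "All randomized, non-withdrawn patients will be included in the ITT analysis". A per-protocol analysis is planned alongside it.

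Section 15.6 explains the step from 202 to 230 patients as an allowance for drop-out, "since some subjects may not be able to complete the protocol and will be withdrawn from the study". The synopsis promises ITT, but its sample-size text puts drop-out and inability to complete the protocol into one allowance.

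Section 12.4 has two rules. On stopping treatment: "Subjects who undergo early discontinuation of the study treatment will not be replaced, and such events will be accounted for by intention-to-treat analysis". On leaving the study: "Subjects who withdraw from the study will be replaced with a new subject that will be independently randomized".

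Section 13 lists, among protocol violations, "Early termination of temperature management protocol". It then says: "Protocol violations will be accounted for by intention-to-treat analysis". It adds: "Withdrawal of the subject will not be required, as all study procedures are completed within the first visit at the time of LTx".

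Section 12.1 treats failed placement of the esophageal device as stopping treatment: "Subjects will also be discontinued from the study treatment if the study doctor is unable to place the ECD after three attempts". Section 12.3 covers withdrawal from the study separately and allows the subject, the investigator or the sponsor to initiate it.

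**The concern.** The same patient can be inside or outside the primary analysis, depending on which section the analyst follows. Take a patient whose cooling is stopped early. Under 12.4 and 13 the patient is analysed in the assigned arm. Under 15.6 the patient counts as withdrawn, and under 15.3 a withdrawn patient is not in ITT.

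If the second route were followed, patients would be removed after randomisation for a reason that may relate both to treatment and to prognosis. Section 8.2 leaves the anesthesiologist investigators unblinded, and section 12.3 lets an investigator withdraw a subject. Section 2.1 allows hypothermia to be aborted for coagulopathy, a reason that arises in one arm only. Removals could therefore differ by arm.

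Timing matters as well. Section 15 promises a separate SAP only before the final data are analysed, but the interim in 15.5.1 can stop the trial for efficacy at p<0.0054. The set needs to be settled before that look or, if it has passed, before the final analysis.

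**Working it through.** **Step 1: where the conflict arises.** Sections 12.1 and 12.3 distinguish stopping treatment from leaving the study, and 12.4 gives each its own rule. If non-withdrawn in 15.3 has the 12.3 meaning, 15.3 agrees with 12.4. The 15.6 clause breaks this, because it makes inability to complete the protocol a reason for withdrawal.

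**Step 2: which non-completers already have a rule.**
- Failed device placement, adverse event, or protocol violation requiring discontinuation (12.1): treatment discontinuations, kept in ITT by 12.4.
- Early termination of temperature management (13): a violation, kept in ITT.
- Abortion of hypothermia for coagulopathy (2.1): a treatment discontinuation or early termination, kept in ITT by 12.4 or 13.
- Withdrawal of consent (listed in 12.1; leaving the study is covered by 12.3): the one named route that can properly fall under withdrawal.

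Section 15.6 does not say which of these it means, and no section limits withdrawal to withdrawal of consent.

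**Step 3: the plan's own figure.** Reading the 30% reduction as relative, the rates are 68% and 0.70 × 68% = 47.6%. The continuity-corrected two-proportion formula at 80% power and two-sided 0.05 gives 101 per arm, as stated (91 without the correction). The allowance is 230 − 202 = 28 patients, or 28/230 = 12.2%. The sample size is not in dispute.

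**Step 4: what exclusion could do (illustration; the exclusion rates and risks are assumptions).** Assume no true effect, 68% AKI in both arms, 115 randomised per arm, and 10% of the hypothermia arm only withdrawn (w = 11.5) at AKI risk r.

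Apparent hypothermia AKI = (0.68 × 115 − w × r)/(115 − w) = (78.2 − 11.5r)/103.5

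- r = 80%: 69.0/103.5 = 66.7%, a spurious difference of 1.3 points
- r = 90%: 67.85/103.5 = 65.6%, 2.4 points
- r = 100%: 66.7/103.5 = 64.4%, 3.6 points

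The test is the pooled two-sample z-test at the final look only, with critical value 1.967 (two-sided p<0.0492). With d the spurious difference, s0 the pooled and s1 the unpooled standard error (each about 0.064), the tail favouring hypothermia is Φ((d − 1.967·s0)/s1) and the opposite tail is Φ((−d − 1.967·s0)/s1).

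- Favouring hypothermia: 4.0, 5.7, 7.9% (2.5% with no exclusion)
- Favouring control: 1.5, 0.9, 0.6% (2.5% with no exclusion)
- Two-sided total: 5.4, 6.6, 8.5% (4.9% with no exclusion)

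Fourteen withdrawn per arm at equal risk leaves the rate at 4.9%. With 8 withdrawn from hypothermia and 20 from control, all at 90% risk, the error runs the other way: 0.8% favouring hypothermia and 6.4% favouring control.

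**Step 5: power if non-completers are kept.** Assume a fraction f of the hypothermia arm does not complete and has the control risk, so the arm's AKI rate is 0.476(1 − f) + 0.68f. With 115 per arm and p<0.0492, power with and without continuity correction is:
- f = 0: 47.6% AKI, power 85% and 88%
- f = 5%: 48.6%, 82% and 85%
- f = 10%: 49.6%, 77% and 81%
- f = 12.2%: 50.1%, 75% and 79%

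**The case against.** The best defence is that the operative rules agree. Sections 12.1, 12.3, 12.4 and 13 all point to keeping non-completers, and the synopsis says ITT. The discordant words are an aside explaining enrolment, outside the section that defines the analysis set. A reader who lets specific rules override an aside would keep these patients. This stands as an argument about severity: it makes the point a correction to wording rather than a flaw in the design. It does not remove the conflict, because 15.3 itself uses the word withdrawn and 15.6 is where non-completion is called withdrawal.

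Section 15.6 may also mean only some non-completers, for instance patients randomised before device placement who never start treatment. That is possible, since 10.1 lists randomisation before placement, but the text does not say so.

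The outcome is also protected in part. AKI is adjudicated blind from creatinine, and intraoperative non-completion precedes the 72-hour outcome. This limits bias in measuring the outcome, but not bias from removing patients whose prognosis differs. The promised SAP could settle the set, but it need not precede the interim. The reference to withdrawn subjects in 15.5.1 governs the accrual count and does not itself define the interim analysis set.

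A reader might go further and infer that the trial will drop every non-completer, that the result is biased towards hypothermia, or that the false-positive rate roughly triples. The documents support none of these. They give no count, arm split or outcome for withdrawn patients; the direction can reverse; and the move from 2.5% to 7.9% is one tail of a two-sided test under the most extreme risk assumed in that scenario.

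**Conclusion.** The concern holds as an inconsistency that should be fixed. The weight of the text favours keeping non-completers, and one clause in 15.6, acting through 15.3, says otherwise. Up to about 28 patients, the size of the allowance, could move in or out of the primary set depending on the reading.

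Bias is possible and not shown. The illustrative two-sided error of 5.4 to 8.5% rests on no true effect, losses confined to the hypothermia arm, and AKI risks of 80 to 100% in those lost. The conclusion rests on the conflict between sections, not on these scenarios.

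**What to change.** - **15.3:** define ITT as all randomised patients, analysed by assigned arm whether or not the temperature protocol was completed. Exclude only patients who refuse use of their data (including at the re-consent step in 10.2), and report their number by arm.
- **15.6 and synopsis:** delete the words in 15.6 that make non-completers withdrawn from the study, and align the synopsis sample-size text so that non-completion is not counted as drop-out.
- **12.4:** state that a replacement does not remove the original patient from ITT.
- **15.5.1:** use the same set at the interim.

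Non-completion is then examined in the per-protocol analysis already planned. No new data are needed, since 8.2 says that only creatinine before and after surgery is required to adjudicate the outcome. The cost is wording, plus a restated power of about 77-81% with 230 analysed, if 10% of the hypothermia arm does not complete and is assumed to gain nothing from partial cooling.

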4 STUDY DESIGN

4.1 Study Overview

This is a multi-center, single-blind, RCT. 230 subjects are planned. Each subject will have an ECD placed after induction of general anesthesia and undergo LTx with one of two temperature management protocols (Fig. 1). Each subject will receive only one of the two experimental treatments. Subjects will be randomizaed to one of the two treatments. Evaluations will be taken at baseline, and at several intraoperative time points. Data from the electronic medical record will be analyzed post-operatively.

Screening data will be reviewed to determine subject eligibility. Subjects who meet all inclusion criteria and none of the exclusion criteria will be entered into the study.

The following treatment regimens will be used (Fig. 1):

- Experimental treatment Mild hypothermia (34-35 °C). Cooling will be initiated after induction of anesthesia and maintained throughout the anhepatic phase of LTx (Fig. 1). In all feasible cases the surgeon will cover the peritoneal surface over the right kidney, which is exposed during the operation, with ice-cold sponges to enhance cooling of the renal parenchyma. Shortly (15 minutes) after the portal vein is reperfused, the ECD and other standard measures (forced-air, fluid, and table warmers, plus a heated anesthesia circuit) will be used to actively rewarm the patient (expected warming rate ≥ 1 °C/hour). The goal is to achieve normothermia by case end.
- **Control** Normothermia (36.5-37.5 °C). After induction of anesthesia, the ECD and standard warming measures will be used to maintain normothermia throughout the operation.

Total duration of subject participation will be approximately 6-10 hours, which is the duration of surgery. Subjects will be followed up remotely via the electronic medical record (EMR) for 1 year after LTx.

[figure not shown]

Figure 1. Scheme of overall study design showing temperature management protocols.

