5 CRITERIA FOR EVALUATION

5.1 Primary Efficacy Endpoint

The primary efficacy endpoint is the incidence of AKI within 72 hours after LTx. The International Club for Ascites (ICA) 2015 criteria, a revision of the KDIGO criteria for patients with cirrhosis, will be used to define AKI.³³ The definitions are as follows:

- AKI: increase in sCr \ge 0.3 mg/dL within a 48 hour time window, or a percentage increase \ge 50% from baseline, or initiation of RRT.
- **Baseline sCr**: the most recent value of sCr prior to LTx

A predefined subgroup analysis of the primary outcome will be performed in patients undergoing liver transplantation for hepatocellular carcinoma (HCC) with Model for Endstage Liver Disease exception points.

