8 STUDY TREATMENTS

8.1 Method of Assigning Subjects to Treatment Groups

Up to 230 eligible patients will be randomly assigned to the Experimental Treatment (mild hypothermia) or Control (normothermia) groups in a 1:1 ratio using a block randomization scheme with a randomly chosen block size of 6 or 8 for each block. The randomization scheme was developed by Randomize.net and is accessed through a secure web portal.

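### The unadjusted primary test forgoes possible precision, and the logistic model beside it has no stated role, omits baseline creatinine and site, and includes a post-allocation variable

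*Combined protocol and SAP*

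**What the plan says.** Section 15.3 (Analysis of Primary Endpoint) opens with the unadjusted comparison, "The primary outcome (presence or absence of AKI) will be compared between the two arms by two-sample proportion test", and continues: "furthermore, a multiple logistic regression model will be utilized where AKI status (present or absence) is considered as the outcome". The predictors are arm, demographic examples (race, gender, age) and "clinical characteristics (such as local cooling, Model for End-Stage Liver Disease score, etiology of liver disease, etc.) are considered as predictors and/or covariates". Both lists are left open. The Synopsis gives only the proportion test for the primary outcome. Section 15.4 also mentions simple and multiple logistic regression, as a way of finding variables associated with AKI.

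Section 5.1 defines AKI as a creatinine rise of at least 0.3 mg/dL within 48 hours, or at least 50% from baseline, or the start of RRT. Baseline is "the most recent value of sCr prior to LTx". Under Section 8.2 the allocation is revealed only once the patient is in the operating room.

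The Synopsis gives 3 sites. Section 8.1 assigns patients 1:1 "using a block randomization scheme with a randomly chosen block size of 6 or 8 for each block" and names no stratification factor. Section 15 says a detailed SAP, which may modify these analyses, will be written before the final data are analysed.

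**The concern.** Two things are at stake.

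The first is efficiency. Baseline creatinine is needed on every patient to score the endpoint, and it sits inside the endpoint's own threshold. Site is also known before allocation. If these variables predict AKI, a model containing them gives more power from the same patients and allows for chance imbalance. Neither is in the deciding test, and neither is named in the model.

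The second is clarity. Two analyses of one endpoint are planned, and Section 15.5.1 applies its interim and final thresholds to a p value without naming the analysis that produces it. If the analyses disagree, the plan does not say which one counts. An open list leaves the covariates to be chosen later. Including local cooling changes what the arm coefficient means.

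**Working it through.** **Inputs.** From Section 15.6: control AKI 68%, 30% reduction, 80% power, two-sided overall alpha 0.05, 101 per arm. From Section 15.5.1: final threshold 0.0492. The documents do not say how strongly any covariate predicts AKI, so that strength is an assumption and is varied below.

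**Step 1: the plan's own figure.** Read as a relative reduction, the treated rate is 0.68 × 0.70 = 0.476. The difference is 0.204 and the mean rate 0.578.

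- Without continuity correction: n = [1.960·√(2·0.578·0.422) + 0.842·√(0.68·0.32 + 0.476·0.524)]² / 0.204² = (1.369 + 0.575)² / 0.0416 = 90.8, so 91 per arm.
- With continuity correction: (90.8/4)·[1 + √(1 + 4/(90.8·0.204))]² = 100.4, so **101 per arm**, which matches. At alpha 0.0492 the results are 92 and 101.
- A drop of 30 percentage points (68% to 38%) would need only 43, or 49 with correction, so the relative reading is the one used.
- Power of the uncorrected test at 101 per arm: z = (0.204·√101 − 1.369)/0.683 = 0.997, or 84.1% at alpha 0.05, and 83.9% at 0.0492.

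The planned 80% therefore does not depend on adjustment.

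**Step 2: the effect of adjustment.** Trials of 101 per arm were simulated at 68% against 47.6%, alpha 0.0492, one final look, 4,000 runs per row. The adjusted model held arm, two continuous covariates (one prognostic) and site.

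| Assumed odds ratio per SD | Unadjusted | Adjusted | Change (points) |
|---|---|---|---|
| 1.0 | 85.6% | 84.8% | −0.8 |
| 1.25 | 83.3% | 82.9% | −0.4 |
| 1.5 | 85.0% | 85.4% | +0.4 |
| 2.0 | 85.4% | 87.6% | +2.2 |
| 2.7 | 85.0% | 90.0% | +5.0 |

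The standard error of each power is √(0.85·0.15/4000), about 0.6 points. Movement down the unadjusted column is simulation noise, so read the change within each row. The +0.4 at 1.5 is not a demonstrable gain.

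A separate simulation with one covariate plus site gave 85.4% against 84.4% at an odds ratio of 1.0, and 84.8% against 90.1% at 2.72. With assumed site log-odds of −0.5, 0 and +0.5, it gave 85.1% against 85.5% and 86.7% against 91.4%. Testing the standardised risk difference gave the same overall range, −1 to +5 points.

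**Step 3: why baseline creatinine is a natural covariate.** The 0.3 mg/dL criterion is a 50% rise from 0.6 (0.3/0.6), a 30% rise from 1.0 and a 15% rise from 2.0, so the relative rise needed falls as baseline increases. Take an assumed lognormal baseline (median 0.9 to 1.2 mg/dL, log-SD 0.3 to 0.5), a relative rise independent of baseline (log-SD 0.3 to 0.5) and overall AKI of 68%. The definition alone then produces an odds ratio per SD of about 1.25 to 1.7. Against Step 2, that is worth roughly −1 to +2 points. Larger gains need MELD or site to be prognostic as well.

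**Step 4: local cooling.** Sections 4.1 and 8.3 describe it under the experimental treatment only, where feasible. Suppose logit(AKI) = b0 + b1·arm + b2·cooling, with cooling zero in all controls. Controls have b0, experimental patients without cooling b0 + b1, and those with it b0 + b1 + b2. The arm coefficient b1 then compares controls with the experimental patients in whom cooling was not done. That subgroup forms after allocation, so b1 is no longer the randomised comparison.

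**The case against.** The strongest case against is that nothing here is wrong. A two-proportion test is valid under 1:1 randomisation, the sample size was computed for it, and its result is easy to read. That stands, and a reader who infers that the trial is underpowered would be mistaken (Step 1).

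Nor is the plan wholly unadjusted. The same sentence of Section 15.3 supplies an adjusted model with MELD score and etiology, its open list could admit creatinine and site, and details are left to the SAP. This stands in part: an open list with no stated role does not settle which analysis decides, and it still contains local cooling.

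The gain is also conditional. Being tied to the endpoint definition does not make baseline creatinine a strong predictor, and with weak covariates adjustment loses up to about a point. That stands and is reflected in the range.

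A reader might also infer that allocation is unbalanced within sites and the randomisation list should change. The documents do not support this. Section 8.1 does not say whether the list is site-specific, and site sizes are not given. With assumed sizes of 160, 40 and 30 and one unstratified list, a 60:40 or worse split arises in roughly 21–23% of trials at the 40-patient site and 32–33% at the 30-patient site. With assumed site log-odds of 0, +0.5 and −0.5, however, the resulting shift in the risk difference has a median of 0.5 points and a 95th percentile of 1.5. The standard error at 115 per arm is √(0.467/115) = 6.4 points.

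Finally, the footnote to Section 8.3 shows that patients have already been treated, so a change to the deciding test must be tied to the interim rule. That stands, and the fix provides for it.

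**Conclusion.** The point holds as a recommended improvement, not as an error. The deciding test is unadjusted. The logistic model beside it has an undefined role and an open list, names neither baseline creatinine nor site, and names a post-allocation variable.

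At 101 per arm, a fixed model on pre-randomisation covariates changes power by about −1 to +5 points. This rests on 68% against 47.6%, a single final look at 0.0492 and the assumed covariate strengths. The undefined role and the presence of local cooling are visible in the text and rest on no assumption about strength.

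**What to change.** In the SAP, before any unblinded look:

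- Make the deciding analysis a logistic model with arm and a closed list of pre-randomisation covariates: log baseline creatinine, MELD and site. Report it as a standardised risk difference with 95% CI.
- Exclude local cooling and any other variable that arises after allocation.
- State that the 0.0054 and 0.0492 thresholds apply to this analysis, and what is done if the model does not converge. At the interim, 101 patients at the design's mean rate of 0.578 give about 58 with AKI and 43 without, for five terms (arm, two covariates, two for site).
- Show the unadjusted test beside it as supportive.

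If the interim look has already taken place, keep the unadjusted test as deciding and make this model the single pre-specified adjusted analysis.

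The randomisation list need not change. The sponsor should only confirm whether it is site-specific.

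Cost: wording and an agreed interim rule, with no new data. The primary result would depend on a simple model, and about 1 point of power is lost if the covariates turn out not to be prognostic.

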STATISTICS Primary Analysis Plan	Presence or absence of AKI, and the different categories of AKI (Stage 1, 2, or 3 or no AKI), will be summarized as frequency and percentage. The primary outcome (presence or absence of AKI) will be compared between the two arms by a two-sample proportion test. The frequency of different categories of AKI (Stage 1, 2, or 3 or no AKI) will be analyzed by a chi-square test. Intention-to-treat analysis will be performed.
Rationale for Number of Subjects	The incidence of AKI in LTx patients at UCSF is 68%. Considering one interim analysis for efficacy, we estimate a sample size of 101 subjects per arm is needed to detect a 30% reduction in AKI with 80% power at overall $\alpha = 0.05$ (two-tailed). To allow for approximately 10% study drop-out or inability to complete the study protocol, we plan to enroll a total of 230 subjects.

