8.2 Blinding

Due to the objectives of the study, the identity of test and control treatments will not be known to patients. The following study procedures will be in place to ensure single-blind administration of study treatments.

Access to the randomization code will be strictly controlled. The randomization code will not be revealed until the patient has entered the operating room for liver transplantation. The study protocol will be completed in its entirety while the patient is in the operating room under general anesthesia. Therefore, it will be impossible for the patient to know the treatment assignment until the protocol is complete.

No attempt will be made to blind the study doctors (anesthesiologists), who are investigators in the study, to the treatment assignment, as they will be the ones administering and monitoring the temperature protocol during LTx.

Research staff assigned to adjudicate the Primary Outcome (presence or absence of AKI within 72 h of LTx) will be blinded to the treatment assignment and the intraoperative anesthesia record showing the patient's core temperature. Only the preoperative and postoperative values of sCr will be necessary to adjudicate the Primary Outcome.

The study blind will be broken on completion of the clinical study and after the study database has been locked.

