8.3 Formulation of Test and Control Treatments

After induction of general anesthesia, the ECD will be connected to the Gaymar Medi-Therm III Hyper/Hypothermia Machine and tested for leaks according to the manufacturer's instructions. Then, it will be lubricated and placed into the esophagus of the subject in a manner identical to that of the standard OG tube used in LTx surgery.

The standard bladder temperature probe used in LTx operations will be connected to the PATIENT PROBE jack of the Gaymar Medi-Therm III, which will be used in AUTO/Rapid mode.

In both Study Arms (Mild Hypothermia and Normothermia), the subject will be given 2 grams of magnesium (Mg) sulfate IV at the beginning of surgery if the preoperative Mg < 2 mg/dL. This will be done because mild hypothermia may trigger a cold-induced diuresis and loss of electrolytes. Therefore, efforts will be made to keep the Mg normal (1.8-2.4 mg/dL) in both groups. Potassium will also be monitored carefully during surgery and replaced at the discretion of the attending anesthesiologist/study doctor.

Experimental treatment – Mild hypothermia (34-35 °C).

- Cooling will be initiated after induction of anesthesia and maintained throughout the anhepatic phase of LTx (Fig. 1). This will be done by selecting a Set Point temperature of 34.8 °C¹ on the Gaymar Medi-Therm III.
- In all feasible cases the surgeon will cover the peritoneal surface over the right kidney, which is exposed during the operation, with ice-cold sponges (lap sponges soaked in ice water and wrapped around ice cubes) to enhance cooling of the renal parenchyma. Local cooling will be applied to the right kidney beginning approximately 10 minutes prior to the anhepatic phase. The anhepatic phase is defined as application of the inferior vena cava (IVC) clamp and removal of the recipient liver.
- After the portal vein is reperfused, the ECD (by selecting a Set Point temperature of 37 °C on the Gaymar Medi-Therm III) and other standard measures (forced-air, fluid, and table warmers, plus a heated anesthesia circuit) will be used to actively re-warm the patient (expected warming rate ≥ 1 °C/hour). The goal is to achieve normothermia by case end.

Control – Normothermia (36.5-37.5 °C).

• After induction of anesthesia, the ECD (by selecting a Set Point temperature of 37 °C on the Gaymar Medi-Therm III) and standard warming measures will be used to maintain normothermia throughout the operation.

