15 STATISTICAL METHODS AND CONSIDERATIONS

Prior to the analysis of the final study data, a detailed Statistical Analysis Plan (SAP) will be written describing all analyses that will be performed. The SAP will contain any modifications to the analysis plan described below.

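### The logistic model for AKI adjusts for local cooling, which is part of the hypothermia regimen, so its arm term need not estimate the effect of the randomised regimen

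*Combined protocol and SAP*

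**What the plan says.** The primary comparison is unadjusted: "The primary outcome (presence or absence of AKI) will be compared between the two arms by a two-sample proportion test" (Protocol Synopsis, Primary Analysis Plan). Section 15.3 repeats this test and then adds a regression: "a multiple logistic regression model will be utilized where AKI status (present or absence) is considered as the outcome and arms along with demographic characteristics". The clinical terms follow: "clinical characteristics (such as local cooling, Model for End-Stage Liver Disease score, etiology of liver disease, etc.) are considered as predictors and/or covariates".

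Local cooling means packing the right kidney. Section 8.3 lists it under the experimental treatment: "In all feasible cases the surgeon will cover the peritoneal surface over the right kidney, which is exposed during the operation, with ice-cold sponges". Section 4.1 gives its purpose: "with ice-cold sponges to enhance cooling of the renal parenchyma". Section 8.3 has it start about 10 minutes before the anhepatic phase. The control regimen contains no local cooling: "After induction of anesthesia, the ECD and standard warming measures will be used to maintain normothermia throughout the operation" (Section 4.1).

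On timing, Section 8.2 says: "The randomization code will not be revealed until the patient has entered the operating room for liver transplantation". Packing therefore always comes after the arm is known.

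Section 15 leaves detail to a later SAP: "The SAP will contain any modifications to the analysis plan described below". Section 15.4 separately plans logistic regression to look for factors associated with AKI, and a multiple proportional odds model for AKI stage whose covariates it does not name.

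**The concern.** Section 15.3 groups local cooling with MELD score and etiology, as if it described the patient. It is a component of one arm's treatment, delivered after allocation and only where surgery allows. Conditioning on it splits the hypothermia arm by a post-randomisation event that cannot occur in protocol-adherent controls.

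An adjusted arm odds ratio reported under the primary endpoint would naturally be read as the adjusted treatment effect. With local cooling in the model it answers another question: how hypothermia patients who were not packed compare with all controls. It could look weaker than the primary result, or differ from it through selection, with no true conflict between the two analyses.

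**Working it through.** **Inputs from the documents (Section 15.6).** Control AKI 68%; a 30% reduction, read as relative, giving 0.68 × 0.70 = 47.6%; 101 per arm; 80% power; two-sided 0.05.

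**The plan's own figure.** The pooled two-proportion formula gives 90.8 per arm. With the continuity correction, n′ = (n/4)[1 + √(1 + 4/(n × 0.204))]² = 100.4, rounded up to 101. This matches, so the reading of the design rates is right.

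**Assumed, because the documents do not give them.** The share of the hypothermia arm that is packed, and AKI risk by packing status. Other covariates are left out at first.

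**What the arm term estimates.** With local cooling = 0 in all controls, arm and local cooling define three groups and the model has three parameters, so it is saturated:

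arm OR = odds(AKI, unpacked hypothermia) / odds(AKI, control).

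Packed patients do not enter it. Without local cooling, the design arm OR is (0.476/0.524)/(0.68/0.32) = 0.427, log OR −0.850.

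**Case 1: unpacked patients share the arm's risk (precision only).** With m unpacked patients, SE = √[1/(101 × 0.68 × 0.32) + 1/(m × 0.476 × 0.524)].

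| Packed | m | SE | Wald power |
|---|---|---|---|
| covariate not in model | 101 | 0.292 | 83% |
| 50% | 50.5 | 0.353 | 67% |
| 70% | 30.3 | 0.422 | 52% |
| 80% | 20.2 | 0.494 | 41% |
| 90% | 10.1 | 0.665 | 25% |

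The 95% interval is exp(−0.850 ± 1.96 × SE): 0.24–0.76 without the covariate and 0.16–1.13 at 80% packed, around the same odds ratio of 0.43.

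**Case 2: packing works, no selection, 80% packed.** Let packing supply share s of the 20.4-point reduction, with the arm as a whole held at 47.6%. Unpacked risk is u = 0.68 − (1 − s) × 0.204; packed risk is (0.476 − 0.2u)/0.8.

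| s | u | Packed risk | Arm OR |
|---|---|---|---|
| 0 | 0.476 | 0.476 | 0.43 |
| 0.25 | 0.527 | 0.463 | 0.52 |
| 0.50 | 0.578 | 0.451 | 0.64 |
| 1 | 0.680 | 0.425 | 1.00 |

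The regimen odds ratio is 0.43 in every row.

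**Case 3: packing inert, no regimen effect (68% in both arms), 80% packed.** If unpacked patients have 60 / 68 / 80% AKI, packed patients have (0.68 − 0.2u)/0.8 = 70 / 68 / 65%, and the arm OR is 0.71 / 1.00 / 1.88.

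**Case 4: everyone packed.** Local cooling then equals arm. The design matrix has rank 2 for 3 parameters, so no separate arm effect can be estimated.

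**Check with a baseline covariate.** A simulation used 400,000 per arm, 80% packed at random, true log OR −0.46 for systemic cooling and −0.50 for packing, and a covariate with log OR 0.5 per SD. The arm log OR was −0.45 (OR 0.64) with local cooling in the model and −0.86 (OR 0.42) without it.

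**The case against.** The strongest reply is that the plan never says the arm term is the adjusted treatment effect. The covariate list is illustrative, its closing words allow either role, and Section 15.4 gives logistic regression an exploratory purpose in which a treatment component may properly appear. A model with both terms can also describe systemic and local cooling separately, and the regimen effect can be recovered: in a simulation with random packing, the arm coefficient plus 0.8 times the local-cooling coefficient gave −0.861, the same as the model without local cooling. On this view the fault is one of labelling. That stands in part: the point applies only where the arm term is read as the treatment effect. But the model sits under the primary endpoint with arm as a term, and the predictor search has its own place in Section 15.4.

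The direction in Case 2 does hold only without selection. If packing supplies half the benefit (10.2 points), and unpacked patients would have had 55 / 60 / 68 / 75% AKI untreated, then u = 44.8 / 49.8 / 57.8 / 64.8% and the arm OR is 0.38 / 0.47 / 0.64 / 0.87, against a regimen value held at 0.43. The net direction is unknown. The sizes show a mechanism, not a forecast, and the s = 1 row requires systemic cooling to do nothing.

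Exact collinearity would announce itself in the output. Near-collinearity would not: at 90% packed the model fits without complaint, with an SE of 0.665.

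The promised SAP could remove the covariate, but nothing in Section 15 commits it to do so.

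**Conclusion.** The concern holds. As written, Section 15.3 names a post-allocation component of one arm as a covariate beside arm. The arm coefficient then estimates unpacked hypothermia against control. It equals the regimen effect only if AKI risk does not differ by packing within the hypothermia arm, and even then with less precision (SE 0.292 to 0.494 at 80% packed). Otherwise it can move from 0.43 towards 1.00 if packing works, or to either side through selection. The algebra assumes no control is packed and no other covariates; the sizes also rest on an assumed packed share and assumed risks by packing.

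This should be fixed before the final analysis, but it touches only the additional model. The primary proportion test, the sample size and the interim rule stand.

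A secondary point, held with less confidence: Section 8.3 asks for packing where feasible, Section 13 counts failure to pack as a violation, and Section 15.3 builds the per-protocol set from completion of the systemic protocol while excluding violators. Whether an unpacked patient who completed systemic cooling belongs in that set is unclear. If such patients are out and the same model is run there, Case 4 applies.

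**What to change.** In the SAP:

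- Leave local cooling out of any model whose arm term is interpreted as the treatment effect, including the proportional odds model in Section 15.4 if it takes the same covariates.
- Adjust only for pre-randomisation variables. Race, gender, age, MELD score and etiology, all already named, qualify. Fix the full list in place of the open-ended one.
- Report AKI by packing status within the hypothermia arm, labelled exploratory and non-randomised.
- If a predictor search under Section 15.4 keeps local cooling, state that its arm term is not a treatment effect.

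Separately, reconcile Sections 8.3, 13 and 15.3 before the final data are analysed, so that the per-protocol status of an unpacked patient who completed systemic cooling is clear.

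The modelling changes cost only SAP wording, which Section 15 already provides for. Any change to Section 8.3 or 13 would be a protocol amendment needing prior written IRB/IEC approval (Section 17.1). The contribution of local cooling becomes exploratory; packing was not randomised on its own, so no randomised comparison is lost.
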